4.3 Psychosocial Interventions for Methamphetamine Dependence

Combinations of pharmacologic interventions with psychosocial counseling has become a standard approach in drug development trials due to the additive or synergistic efficacy of combined modalities. Methamphetamine users tend to have poor treatment retention, with only 42% completing the course of treatment and nearly 60% relapsed in the year following treatment.¹²⁷ Psychosocial counseling improves treatment retention and thus may be a key element in pharmacologic intervention studies. This is supported by analysis of the smoking cessation literature, in which it was found that adding behavioral therapy to nicotine replacement, doubled the quit rate evident with replacement therapy alone and vice versa. Adding nicotine replacement to behavioral therapy essentially doubled smoking cessation rates.¹²⁷ Similarly, the heroin, cocaine and alcohol addiction treatment literature shows good results from the combination of medication and behavioral interventions.¹²⁸⁻¹³⁰ The combination of behavioral interventions with methadone treatment results in reduced opiate use and increased attendance/retention rates.^{25,131-139} Overall, the existing evidence for combining medication and behavioral interventions indicates the efficacy of this approach in the treatment of methamphetamine dependence.¹⁴⁰

4.4 Psychosocial Intervention

In contrast to opioid dependence treatment trials in which medication effects are large, methamphetamine dependence prevention trials require psychosocial interventions that are robust enough to make participants return to the clinic. Studies with inadequate psychosocial support may suffer from excessive early termination, which distorts conclusions regarding the efficacy of medication.³¹ Thus, use of adequate CBT strategies is very important. CBT was developed during the 1980's and is based on a set of social learning theory techniques. These techniques refer to a wide range of strategies designed to prevent relapse to addictive behaviors, including cocaine use, heavy alcohol use, overeating, and tobacco smoking. Common among the varieties of CBT strategies is the primary focus on maintenance in the habit change process, i.e., preventing occurrence of initial lapses after one has embarked on a program of habit change, and/or preventing any lapse from escalating into a total relapse.¹⁴¹ The Matrix Model of Relapse Prevention Counseling¹⁴² has been used by NIDA DPMC in several clinical trials evaluating medications for methamphetamine dependence. The efficacy of this Model in the treatment of methamphetamine dependence has been demonstrated.¹⁴⁰ Overall, CBT is a feasible strategy that is generally well accepted by patients seeking treatment, and will be used in this study.

5 STUDY OBJECTIVES

5.1 Primary Objective

The primary objective of this study is to assess the efficacy of bupropion in reducing methamphetamine use in subjects with methamphetamine dependence who report using methamphetamine 29 or less days during the 30 day prior to signing consent. It is hypothesized that bupropion, compared to placebo, will be associated with an increase in the proportion of subjects who achieve abstinence (confirmed by at least two methamphetamine-negative urines and no methamphetamine-positive urines) each week during the last two weeks (Weeks 11 and 12) for non-daily users as the primary outcome.

5.2 Secondary Objectives

Secondary objectives include but are not limited to:

- 1. Assessing the efficacy of bupropion in reducing methamphetamine use in subjects with methamphetamine dependence who report using methamphetamine 18 or less days during the 30 day prior to signing consent.
- 2. Determining the safety of bupropion in the study population.
- 3. Assessing the efficacy of bupropion in other measures of success in the reduction of methamphetamine use determined by methamphetamine qualitative and quantitative urinalysis, self-report of use, and combinations of the two.
- 4. Assessing the efficacy of bupropion in the reduction in the severity of methamphetamine dependence (assessed by ASI-Lite and self and observer scored CGI), craving (assessed by BSCS), ADHD symptoms, (assessed by AISRS scores), and severity of depression (assessed by HAM-D) as compared to placebo control.

- 5. Assessing the rates of continued abstinence 4-weeks after completing the investigational product dosing period.
- 6. Assessing the effects on HIV risk taking behaviors.
- 7. Assessing the effects of bupropion on study retention.
- 8. Evaluating genetic variance and change in expression profiles on clinical outcomes including efficacy and safety.
- 9. Assessing the association of BDNF levels with clinical success and the influence of bupropion on BDNF levels.

6 IND HOLDER

This study will be conducted under an IND held by NIDA.

7 STUDY SITES

The trial will be conducted as a multi-center study at 5 or more clinical sites.

8 STUDY DESIGN

This is a double-blind, placebo-controlled, parallel-group design study in which, after screening and a 2-week baseline period, 200 participants will be randomly assigned to either receive placebo or bupropion (100 subjects per group) daily for 12 weeks, with a follow-up assessment 4 weeks after completion of study interventions. Adaptive randomization will be used to balance study intervention groups based on site, methamphetamine use (18 or less *versus* 19-29 days out of 30 days prior to signing consent), severity of depression symptoms (HAM-D score ≤ 12 *versus* >12), and presence of Adult ADHD.

9 SUBJECT SELECTION

Target randomization includes 200 males and females with methamphetamine dependence (approximately 100 subjects per group). Entry into this study is open to both men and women and to all racial and ethnic subgroups. An attempt will be made to randomize at least 30% females. Potential study subjects will be recruited from a variety of sources. The primary source will be individuals seeking treatment for methamphetamine dependence via referrals from local treatment providers and word of mouth from subjects already participating in the trial. Additional individuals will be recruited from the community by means of advertising in local media. Recruitment advertisements will be approved by NIDA and then by each site's Institutional Review Board (IRB).

9.1 Inclusion Criteria

Participants must:

- 1. Be males and/or females, between 18 and 65 years-of-age, inclusive.
- 2. Have a DSM-IV diagnosis of methamphetamine dependence as determined by MINI.
- 3. Have at least 1 amphetamine or methamphetamine positive urine specimen (> 500 ng/mL) after the start of screening and before randomization, or provide collateral information to verify recent use if a positive urine sample can't be obtained.
- 4. Report using methamphetamine for 29 or less days during the 30 day period prior to signing consent using the Timeline Follow-back method.
- 5. Be willing and able to comply with study procedures.
- 6. Be able to verbalize understanding of consent forms, able to provide written informed consent for both the main study and genetics study, and verbalize willingness to complete study procedures.
- 7. Be seeking treatment for methamphetamine dependence.
- 8. If female, have a negative pregnancy test during screening and on the first day of investigational product administration and agree to use of one of the following methods of birth control:
 - a. prescription oral contraceptive
 - b. contraceptive patch
 - c. barrier (diaphragm or condom) with spermicide
 - d. intrauterine progesterone or non-hormonal contraceptive system
 - e. levonorgestrel implant
 - f. medroxyprogesterone acetate contraceptive injection
 - g. complete abstinence from sexual intercourse and agree to use another method should sexual activity commence
 - h. hormonal vaginal contraceptive ring
 - i. contraceptive sponge
 - j. surgical sterilization
 - k. partner is surgically sterile
 - 1. be post menopausal for one year

9.2 Exclusion Criteria

Participants must not:

1. Have current dependence, defined by DSM-IV criteria, on any psychoactive substance (e.g., opioids) other than methamphetamine, nicotine, alcohol or marijuana or have physiological

dependence on alcohol or a sedative-hypnotic (e.g., a benzodiazepine) requiring medical detoxification.

- 2. Have a current or past history of seizure disorder, including alcohol- or stimulant-related seizure, or significant family history of idiopathic seizure disorder.
- 3. Currently be using drugs that lower seizure threshold.
- 4. Have a history of head trauma that resulted in neurological sequelae (e.g., loss of consciousness greater than 5 minutes, or that required hospitalization).
- 5. Have psychiatric disorders, such as major current depression, psychosis, bipolar disorder, organic brain disorder, or dementia as assessed by the MINI interview, or medical disorder, any of which require an excluded medication (e.g., antidepressant, neuroleptic, systemic corticosteroid, xanthine) or which would make medication compliance difficult. Have had electroconvulsive therapy within the past 90 days before screening.
- Have a current suicidal ideation/plan as assessed by the MINI interview or HAM-D question #3. Current is identified as within the past 30 days.
- 7. Have a current or past history of anorexia nervosa or bulimia disorder.
- 8. Have serious medical illnesses or neurological disorders including, but not limited to, uncontrolled hypertension (See NIDA Guidelines on Hypertension in the Operations Manual, stage 1 hypertension allowed, but not stage 2 hypertension), significant heart disease (including myocardial infarction within one year of enrollment), angina, hepatic or renal disorders, renal insufficiency (plasma creatinine > 1.7 mg/dL), Parkinson's disease, active syphilis that has not been treated or refuse treatment for syphilis (see note), or have had therapy with any opiate-substitutes (methadone, LAAM, buprenorphine) within 2 months of enrollment, or any serious, potentially life-threatening or progressive medical illness other than addiction that may compromise subject safety or study conduct. Any ECG/cardiovascular abnormality (e.g., QTc interval prolongation > 450 milliseconds in men or 480 milliseconds in women), which in the judgment of the investigator is clinically significant.
- 9. Have diabetes with unstable control of blood glucose and have any incidence of hypoglycemia in the past year before screening.
- 10. Be mandated by the court to obtain treatment for methamphetamine-dependence where such mandate required the results of urine toxicology tests to be reported to the court.
- 11. In the opinion of the investigator, be expected to fail to complete the study protocol due to probable incarceration or relocation from the clinic area.
- 12. Be undergoing HIV treatment with antiviral and/or non-antiviral therapy since these drugs may increase the bupropion levels. The following list of HIV treatment/medications may be

used: Norvir, Reyataz, Truvada, Videx, Viread, Androgel and Trizovir. Note: Any HIV medication not on this list should be approved by the medical monitor.

- 13. Have known or suspected hypersensitivity to bupropion.
- 14. Be using bupropion or any medication that could interact adversely with bupropion, within the following times of beginning of administration of bupropion based on the longest time interval of A, B, and C, below or as otherwise specified:
 - A) Five half lives of other medication or active metabolite(s), whichever is longer;
 - B) Two weeks; or
 - C) Interval recommended by other medication's product labeling.

Medications that fall into this category include:

- a. Bupropion (Wellbutrin[®], Zyban[®]) used during the past 30 days
- b. All antidepressants
- c. Neuroleptics
- d. Systemic corticosteroids
- e. Xanthines, i.e., theophilline, theophilline sodium glycinate and aminophylline
- f. Antiretrovirals including nelfinavir, and efavirenz
- g. Tramadol (Ultram, Ultram Extended Release)
- 15. Have participated in any experimental study within 8 weeks (the nature of excluded studies may be discussed with NIDA investigators).
- 16. Be pregnant or breast feeding.
- 17. Have clinically significant laboratory values (outside of normal limits), in the judgment of the investigator.
- 18. Have liver function tests greater than 3 times the upper limit of normal.
- 19. Have active tuberculosis (positive tuberculin test and confirmatory diagnostic chest x-ray).
- 20. Have a diagnosis of adult (i.e., 21 years or older) asthma, or chronic obstructive pulmonary disease (COPD), including those with a history of acute asthma within the past two years, and those with current or recent (past 3 months) treatment with inhaled or oral beta-agonist or steroid therapy (because of potential serious adverse interactions with methamphetamine), or have an FEV1 <70 %.

Notes on inclusion/exclusion criterion: Although AIDS is an exclusion criteria, a positive antibody titer to HIV is not. If subjects ask about HIV testing during screening, they will be referred to an appropriate clinic that offers this service.

Prospective subjects who are positive for syphilis by the RPR test will have a fluorescent treponemal antibody absorbent assay (FTP-abs) or microhemagglutinin assay-Treponema pallidum (MHA-TP) confirmatory test performed. If this test is positive, prospective subjects must be treated for syphilis. If the prospective subject can provide evidence that they have been previously treated for syphilis or undergoes treatment for syphilis, they can be enrolled upon providing proof of successful treatment for syphilis.

The infectious disease panel for hepatitis and tuberculosis is performed as an aid to determine if the prospective subject has active hepatitis or tuberculosis. Either will exclude the prospective subject from participation according to exclusion criterion number 8 (serious medical illnesses) or number 19 (have active tuberculosis). All subjects who test positive for tuberculosis will be referred and scheduled to have a chest X-ray. Those that do not actually have tuberculosis will not be excluded from the study. Those that show a positive chest X-ray for tuberculosis will be excluded from the study. Prospective subjects who test positive for hepatitis will be evaluated by the site investigator for eligibility. Those subjects will be excluded if they have acute hepatitis or chronic active hepatitis, based on symptoms serology, and/or abnormal liver functions. Subjects who test positive for hepatitis will be referred for treatment as well as those who show positive chest X-ray for tuberculosis.

If any test results are positive subject will be notified of positive and confirmatory test results and will be referred to treatment.

[figure not shown]
Methamphetamine induced psychosis does not exclude a subject from the study, however the presence of current psychotic symptoms will exclude a subject from the study until clinically stabilized.

10 INVESTIGATIONAL PRODUCTS

10.1 Bupropion SR

Bupropion SR tablets, 150 mg, and matching placebo will be supplied by Murty Pharmaceuticals, Inc., (Lexington, KY) under a contract with NIDA. GSK's Zyban (bupropion) SR tablets, 150 mg, will be film-coated by Murty Pharmaceuticals to mask information on tablet surface. Matching placebo will be manufactured by Murty Pharmaceuticals. Data show that the film coating has negligible effect on the dissolution of Zyban SR tablets.

Bupropion's chemical name is (\pm) -1- (3-chlorophenyl)-2-[(1,1-dimethylethyl)amino]-1propanone hydrochloride and has a molecular weight of 276.2. The structural formula is:

10.2 Placebo Control

Identically appearing placebo control tablets will be prepared by Murty Pharmaceuticals.

10.3 Dispensing Investigational Products

Murty Pharmaceuticals will distribute the investigational products packaged in HDPE bottles with child-resistant closure as a 10-day supply to investigators or designated Research Pharmacists at the clinical sites for dispensing to subjects. Used and unused investigational products will be collected and inventoried each week and an investigational product compliance CRF will be completed.

Investigational products will be dispensed to subjects once per week at the first clinic visit of the week. Investigational products will be distributed directly to the subject by the investigative staff depending upon local site procedures. The subject will be thoroughly instructed on how to administer investigational products.

Subjects will be instructed to store investigational products at room temperature without exposure to direct sunlight. Subjects will be instructed to consume the morning dose between 8:00 and 10:00 a.m. and the evening dose between 4:00 and 6:00 p.m. The exact time of the morning and evening doses may vary across patients depending on their schedules, but should be maintained constant for a particular individual. Subjects will be asked to refrain from taking the morning dose on the day during Week 6 and Week 12 that they are scheduled for a blood draw for bupropion levels. At these visits, subjects will be administered their daily dose in the clinic after blood collection. Administration of the daily dose in divided doses of maximum 150 mg twice daily, at least 8 hours apart, should minimize the risk of seizures. Unused investigational products will be collected and inventoried each week.

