11 INTERVENTIONS

11.1 Investigational Products

Subjects assigned to receive bupropion hydrochloride SR will receive 150 mg every day for the first 3 days of dosing which will be increased to 300 mg daily (one tablet twice a day) for the duration of dosing period until the final dose taper. The dose will be tapered to 150 mg every day for 3 days until termination or the last scheduled day of the 12-week intervention period. Subjects will be informed that they must taper the dose for three days before stopping the investigational products completely in the event that they decide to terminate from the study prematurely. Subjects assigned to the placebo group will receive matched placebo on the same schedule as the bupropion group. Subjects will be instructed to take investigational products at least 8 hours apart when taking investigational products twice daily and not to take two tablets at once if a dose is missed. During the last 3 days of study interventions during Week 12 or before termination, subjects' investigational products will be tapered down to 150 mg (or equivalent placebo) each day by taking only one tablet per day.

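### The dosing windows in 10.3 are not tied to the 8-hour minimum interval: read alone they admit doses 6 hours apart, which 10.3 and 11.1 forbid

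*Protocol*

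**What the plan says.** Section 10.3 of the protocol sets the times of day: "Subjects will be instructed to consume the morning dose between 8:00 and 10:00 a.m. and the evening dose between 4:00 and 6:00 p.m". It leaves the choice within those windows to the subject's schedule and asks for consistency within each person once the times are chosen ("The exact time of the morning and evening doses may vary across patients depending on their schedules, but should be maintained constant for a particular" …).

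Later in the same paragraph the protocol says that the daily amount is to be split into doses at least "8 hours apart, should minimize the risk of seizures". Section 11.1 turns the spacing into an instruction to subjects: "Subjects will be instructed to take investigational products at least 8 hours apart when taking investigational products twice daily".

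Twice-daily dosing covers most of the intervention phase. Section 11.1 has one tablet a day for the first 3 days, "which will be increased to 300 mg daily (one tablet twice a day) for the duration of dosing period until the final dose taper", and the taper takes up the last 3 days.

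For the Week 6 and Week 12 plasma samples, 10.3 asks subjects to hold the morning dose; at those visits "subjects will be administered their daily dose in the clinic after blood collection". Sections 13.3 and 13.6.9 repeat that the sample precedes the morning dose. None of these sections refers back to the windows or to the interval.

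**The concern.** The windows and the interval are two limits on the same pair of times, and they do not describe the same set of pairs. A subject who takes in only the clock windows can follow them exactly and still dose closer together than the interval rule allows. Because the subject is also told to keep individual times constant, a short pairing would be repeated daily rather than happen once.

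What is at stake is clarity in a safety instruction. Section 10.3 gives seizure risk as the reason for spacing the doses, and section 4.2.5 lists addiction to stimulants among the circumstances associated with a higher seizure risk. That describes the enrolled population. Sites draft subject instructions from this text, so limits that disagree should not stay in it.

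**Working it through.** **Inputs**

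- Morning window: 08:00 to 10:00 (10.3).
- Evening window: 16:00 to 18:00 (10.3).
- Minimum interval: 8 hours (10.3 and 11.1).
- Twice-daily period: after the first 3 days and before the final 3-day taper of a 12-week course (11.1).

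**Daytime separation**

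Let the morning dose be at 08:00 + m and the evening dose at 16:00 + e, with m and e each between 0 and 2 hours. Then

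separation = (16 + e) − (8 + m) = 8 + (e − m) hours.

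| Case | Morning | Evening | Separation |
|---|---|---|---|
| Shortest (m = 2, e = 0) | 10:00 | 16:00 | 6 h |
| Start to start (m = 0, e = 0) | 08:00 | 16:00 | 8 h |
| End to end (m = 2, e = 2) | 10:00 | 18:00 | 8 h |
| Longest (m = 0, e = 2) | 08:00 | 18:00 | 10 h |

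The protocol's 8 hours is reproduced when the two doses sit at the same relative position in their windows. The separation is below 8 hours whenever e is less than m, that is, whenever the evening dose falls relatively earlier in its window than the morning dose does. The largest shortfall is 8 − 6 = 2 hours.

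**Can both instructions be met?** Yes. For any m between 0 and 2, choosing e equal to or greater than m gives at least 8 hours, and such an e always exists. No permitted morning time leaves a subject unable to comply.

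**Overnight separation**

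The shortest is 18:00 to 08:00 = 14 hours and the longest is 16:00 to 10:00 = 18 hours. Only the daytime gap is in question.

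**Duration**

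For a subject who completes dosing, 12 × 7 = 84 days, less 3 at the start and 3 at the end, leaves 78 days of twice-daily dosing. That is the period over which a constant short pairing could be repeated.

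**The case against.** The strongest reply is that the instructions are cumulative. The windows say when in the day to dose, and the interval says how far apart. A subject dosing at 10:00 and 16:00 satisfies the first and breaks the second, so the protocol taken as a whole does not permit a 6-hour gap. The two windows are offset by exactly 8 hours at both ends, which suggests that they were built with the interval in mind. The spacing rule is stated twice, 10.3 promises thorough instruction on administration, and the Operations Manual, which is not available here, may already link the two times. Section 4.2.5 also rests seizure protection on the ceiling on total daily dose, on excluding predisposed subjects and on prohibiting certain medications, not on spacing alone.

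Most of this stands. It rules out calling the text impossible to follow, and it lowers the severity. It does not remove the fault: the window sentence carries no condition, and the protocol relies on the reader to notice that a later sentence narrows it.

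Two stronger readings are tempting and are not supported:

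- **That the instructions conflict over half of the permitted range.** Giving every pair of minutes in the two windows equal weight, about half fall under 8 hours. That weighting is arbitrary. It ignores the interval instruction that subjects also receive, and nothing in the protocol says how subjects will choose. It predicts no behaviour and should not be used.
- **That blood-draw days make the gap shorter still.** The protocol gives no draw times, so whether the held dose falls outside its window cannot be known. The interval rule in 11.1 has no exception for those days. At Week 12 the point also depends on the visit: 13.3 prefers the first visit of the week, while the footnote to Table 1 places the sample at the last visit, when a completer would be on the once-daily taper and the interval would not arise. All that can be said is that the text does not mention how the windows and the interval apply when the dose is held.

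**Conclusion.** The point holds in a limited form. The windows in 10.3 are not conditioned on the interval in 10.3 and 11.1. Read alone they admit 6 to 10 hours between doses, and so include pairs up to 2 hours short of the stated minimum. Both instructions can be met together from every permitted morning time.

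The result is clock arithmetic on the stated windows and needs no assumption about how subjects behave. How often a short pairing would occur cannot be estimated from the protocol. No outcome measure, analysis population, power figure or error rate depends on it. It merits a minor safety-wording amendment and is not a reason to hold the trial or change its design.

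**What to change.** Reconcile the window sentence in 10.3 with the interval statements in 10.3 and 11.1, so that no pair of times allowed by one is forbidden by another. State that the reconciled text also applies on the blood-draw days when the morning dose is held. Carry the same wording into the subject instructions, and check that the Operations Manual agrees. Which text governs is for the clinical team; no time or interval is proposed here.

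The cost is a few words in 10.3 and 11.1 and in the subject instructions, as a minor amendment. Assessments, data collection and analyses do not change.
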